10 MAMMOGRAPHIC IMAGE LIBRARY

The trial will generate a library of anonymised mammogram images. The aim of any future image studies would be to identify potential radiological features that might predict cases likely to progress or identify early signs of progression.

Sites will prospectively collect the raw image data that will be anonymised with the patients Trial Number (TNO) and transferred securely to Royal Surrey Hospital in accordance with the radiology manual.

The image library is maintained and managed by the NCCPM based at Royal Surrey County Hospital will undergo full and regular backup to a remote secure facility.

Page **27** of **48** Version 4.0, 15th March 2016

Participating sites which do not use Picture Archiving Computer Stores or an equivalent platform, should submit anonymised images for review on CD via post to the National Coordinating Centre for the Physics of Mammography (NCCPM) based at Royal Surrey County Hospital, including the patient's TNO, date of birth and date of mammogram only as identifiers.

11 SAMPLE COLLECTION

11.1 Tumour Paraffin Blocks

Paraffin embedded tumour blocks will be collected for translational research. Please be aware that it will be the responsibility of the local site research team to obtain their patient's pathology material if the material is stored at a separate site to the randomising hospital.

It is appreciated that in some instances there may insufficient diagnostic material available for research purposes. If the local pathology team are concerned that there is insufficient tissue available for research, this should be communicated to the LORIS Trial Office.

The site research team may request the return of tumour blocks collected as part of the trial at any time by submitting a request to the Trial Office.

11.1.1 Primary Diagnostic Core Biopsies

The patient's diagnostic paraffin embedded tumour block(s), (small volume core biopsy and Vacuum Assisted Core Biopsy (VACB) or Vacuum Assisted Core Biopsy (VACB) alone as first line diagnostic approach or small volume biopsy or VACB plus open diagnostic surgical biopsy (without clear margins) or open diagnostic surgical biopsy (without clear margins)) from study entry will be requested Samples should be sent to the Edinburgh Cancer Research Centre in accordance with the LORIS Pathology and Sample Collection Guidelines. Please note that if a patient had multiple biopsies performed, all biopsy tumour blocks will be requested.

A core will be removed from the diagnostic block and any remaining tissue will be returned to the local pathologist.

In cases where the patient had multiple biopsies, there is no requirement to send the tissue block of those samples that contained no DCIS.

11.1.2 Surgical Excisions

Sites will be requested to forward representative tumour blocks from the surgical resection specimens to Edinburgh Cancer Research Centre in accordance with the LORIS Pathology and Sample Collection Guidelines.

A copy of the associated pathology report will be requested for each patient, this should be anonymised to contain only the patient's unique LORIS TNO and returned to the Trial Office.

The blocks will be retained at the Edinburgh Cancer Research Centre for research purposes.

In cases where no DCIS was evident in the surgical sample, there is no requirement to send the surgical sample.

11.1.3 On-Study Diagnostic Biopsies

Sites are requested to forward representative tumour blocks from all future diagnostic blocks to Edinburgh Cancer Research Centre in accordance with the LORIS Pathology and Sample Collection Guidelines.

The blocks will be retained at the Edinburgh Cancer Research Centre for research purposes.

12 ADVERSE EVENT REPORTING

The collection and reporting of AEs will be in accordance with the Research Governance Framework for Health and Social Care and the requirements of the National Research Ethics Service (NRES). Definitions of different types of AE are listed in Appendix 1. The Investigator should assess the seriousness and causality (relatedness) of all AEs experienced by the patient (this should be documented in the source data) with reference to the protocol.

12.1 Reporting Requirements

12.1.1 Adverse Events

AEs (see Appendix 1 for definition) are commonly encountered in patients undergoing treatment for DCIS. The safety of these treatments is already well characterised, therefore only related AEs experienced as a direct result of the trial protocol will be reported.

12.1.2 Serious Adverse Events

Investigators should report related AEs that meet the definition of an SAE (see Appendix 1 for definition) and are not excluded from the reporting process as described below.

12.1.2.1 Events that do not require reporting on a Serious Adverse Event Form

The following events should not be reported on an SAE Form:

- Hospitalisations for:
 - Protocol defined treatment, as this information is captured elsewhere on the CRF
 - Pre-planned elective procedures (including breast reconstruction, as this information is captured elsewhere on the CRF)
 - Treatment for progression of the patient's DCIS or breast cancer, as this information is captured elsewhere on the CRF
- Progression or death as a result of the patient's DCIS or breast cancer, as this information is captured elsewhere on the CRF

12.1.2.2 Expected Serious Adverse Events

We are not expecting any SAEs to occur as a result of participation in this study. The following are regarded as expected SAEs for the purpose of the study and should not be reported on an SAE Form, as this information will be captured elsewhere on the CRF:

- SAEs relating to radiotherapy
- SAEs relating to breast reconstruction
- SAEs relating to adjuvant treatment for breast primary cancer or recurrence
- Hematoma, wound infection or seroma, as a result of primary breast surgery

This is not an exclusive list and Investigators should only report SAEs which are attributable to the study protocol.

12.1.3 Reporting Period

Details of all related SAEs (except those listed in Section 12.1.2.1 and 12.1.2.2 above) will be documented and reported from study entry until 5 years-post randomisation. This extended reporting period should be sufficient for all harm associated with the trial protocol to be captured however, if a related SAE is identified after this period, the event should be reported to the Trial Office.

Page **29** of **48** Version 4.0, 15th March 2016

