4 ELIGIBILITY

The following criteria are applicable in order for a patient to be registered into the study. Patients will only be deemed eligible for randomisation following confirmation of low risk disease by the trial's Central Histopathology Review team.

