If a patient has been diagnosed locally with non-high grade DCIS by small volume biopsy only (14-gauge or by a 13-gauge hand-held device), they should be invited to consent to and undergo a VACB as part of their registration into the study, to confirm the local diagnosis of non-high grade DCIS. If local reporting confirms non-high grade DCIS, all of the histology slides from all biopsies should then be submitted for Central Histopathology Review (see Section 6.1.3 Submitting Slides for Central Histopathology Review).

Patients diagnosed with non-high grade DCIS by open diagnostic surgical biopsy who meet the eligibility criteria specified, may be approached about the trial and consented for registration. These patients will not need to undergo a VACB procedure.

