5.5 Informed Consent

It is the responsibility of the Investigator or delegate to obtain written informed consent for each patient prior to performing any trial related procedure. The Investigator may delegate responsibility for obtaining written informed consent to other appropriate members of the site research team, for example Consultant Radiologists, Radiographers, Clinical Nurse Specialists and Research Nurses who are appropriately trained in obtaining informed consent and in Good Clinical Practice (GCP). Delegation of responsibility for obtaining written informed consent must be indicated appropriately on the Site Signature and Delegation Log (SS&DL).

Patient consent will be undertaken in two stages for all patients randomised into the trial; consent for registration (to allow Central Histopathology Review of all of the diagnostic slides) followed by consent for randomisation. There are three different Patient Information Sheets (A, B and C) and corresponding Informed Consent Forms (A, B and C) for this purpose (see previous Flowchart 1: Patient Pathway to Randomisation).

Patient Information Sheet A is intended for those patients who have been diagnosed locally via small volume biopsy only. The information sheet covers both the additional investigation of VACBs plus subsequent Central Histopathology Review of all of the diagnostic slides in the event that the VACBs confirm the local diagnosis of low or intermediate grade DCIS when reviewed by the local pathologist.

Patient Information Sheet B is intended for those patients who have been diagnosed locally via VACB or by open diagnostic surgical biopsy (with or without prior small volume biopsies or VACBs). This information sheet covers the Central Histopathology Review.

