7.1.7 Related Adverse Event Review

Protocol-related AEs will be collected annually on the CRF from years 1-5. Any persisting, protocol-related adverse effects will be reported annually on the CRF from years 6-10. Serious Adverse Events (SAEs) will be reported from study entry until 5 years post-randomisation in accordance with Section 16 Adverse Event Reporting.

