7.2.5 Investigations and Treatment of Ipsilateral Breast Disease

Please see Flowchart 2: Investigation Algorithm, later in this section.

Investigational biopsies will be taken in the Active Monitoring arm patients, as deemed appropriate by the site research team. In the case of suspected new disease in the ipsilateral breast, the histology slides will be submitted to the Trial Office for Central Histopathology Review (as for the diagnostic slides pre-study entry), in accordance with the LORIS Pathology and Sample Collection Guidelines.

The outcome of the Central Histopathology Review will be reported as either continue Active Monitoring or discontinue Active Monitoring. If there is no change in DCIS morphology, or the patient is confirmed to have additional low risk DCIS or benign disease, the patient will continue with Active Monitoring. If DCIS other than low risk or if invasive disease is confirmed, the patient will discontinue Active Monitoring and should be treated according to local protocol.

The outcome of the Central Histopathology Review will be notified via email to the main contact, reporting pathologist and nominated lead pathologist within 7 days of the slides being received by the Trial Office.

Details of all investigations (regardless of outcome) and subsequent treatment will be collected on the CRF.

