12.2 Reporting Procedure

12.2.1 Site

12.2.1.1 Adverse Events

Related AEs experienced from study entry until 5 years post-randomisation should be reported in the AE section of the CRF.

AEs will be reviewed using the Common Terminology Criteria for Adverse Events (CTCAE), version 4.0 (see Appendix 2). Any related AEs experienced by the patient but not included in the CTCAE should be graded by an Investigator and recorded on the CRF using a scale of (1) mild, (2) moderate or (3) severe. For each sign/symptom, the highest grade observed since the last visit should be recorded.

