23 APPENDIX 1 – DEFINITION OF ADVERSE EVENTS

Adverse Event

Any untoward medical occurrence in a patient or clinical trial subject participating in the trial, which does not necessarily have a causal relationship with the treatment received.

Comment:

An AE can therefore be any unfavourable and unintended sign (including abnormal laboratory findings), symptom or disease temporally associated with the use of a medicinal product, whether or not related to the medicinal product.

Related Event

An event which resulted from the administration of any of the research procedures.

Serious Adverse Event

An untoward occurrence that:

- Results in death unrelated to the original DCIS diagnosis
- Is life-threatening*
- Requires hospitalisation** or prolongation of existing hospitalisation
- · Results in persistent or significant disability or incapacity
- Consists of a congenital anomaly/ birth defect
- Or is otherwise considered medically significant by the Investigator***

Comments:

The term severe is often used to describe the intensity (severity) of a specific event. This is not the same as serious, which is based on patients/event outcome or action criteria.

- * Life threatening in the definition of an SAE refers to an event in which the patient was at risk of death at the time of the event; it does not refer to an event that hypothetically might have caused death if it were more severe.
- **Hospitalisation is defined as an unplanned, formal inpatient admission, even if the hospitalisation is a precautionary measure for continued observation. Thus, hospitalisation for protocol treatment (e.g. line insertion), elective procedures (unless brought forward because of worsening symptoms) or for social reasons (e.g. respite care) are not regarded as an SAE.
- *** Medical judgment should be exercised in deciding whether an AE is serious in other situations. Important AEs that are not immediately life threatening or do not result in death or hospitalisation but may jeopardise the subject or may require intervention to prevent one of the other outcomes listed in the definition above, should be considered serious.

Unexpected and Related Event

An event which meets the definition of both an Unexpected Event and a Related Event.

Unexpected Event

The type of event that is not listed in the protocol as an expected occurrence.

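### The related AE/SAE window opens at an undefined study entry, which on the protocol's main usage comes after the vacuum biopsy the trial adds for women diagnosed by small volume biopsy only

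*Protocol*

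**What the plan says.** **The window.** Section 12.1.3 states that related SAEs, apart from listed exclusions, "will be documented and reported from study entry until 5 years-post randomisation". Section 12.2.1.1 says "Related AEs experienced from study entry until 5 years post-randomisation should be reported in the AE section of the CRF". For SAEs, section 7.1.7 (Surgery arm) repeats "will be reported from study entry until 5 years post-randomisation", and section 7.2.8 does the same for Active Monitoring. Section 12.1.3 extends the window in one direction only: a related SAE identified after 5 years should still be reported. It adds that the period should be enough to catch all harm associated with the protocol.

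**The procedure.** Of women diagnosed by small volume biopsy only, section 5.2 says "they should be invited to consent to and undergo a VACB as part of their registration into the study". Section 5.3 requires consent before the VACB wherever it is not standard local practice. On Patient Information Sheet A, section 5.5 says "The information sheet covers both the additional investigation of VACBs plus subsequent Central Histopathology Review of all of the diagnostic slides".

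**What counts as related.** Appendix 1 defines a related event as "An event which resulted from the administration of any of the research procedures".

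**Entry criteria.** Section 4 opens with "The following criteria are applicable in order for a patient to be registered into the study". The third inclusion criterion is the histological confirmation, which for this group comes from the small volume biopsy plus the VACB.

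**The concern.** The VACB under Form A is an invasive procedure that some women have only because of the trial. Harm from it fits the protocol's own definition of a related event. A reporting window that opens after the procedure cannot be relied on to collect that harm, whatever its length afterwards.

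What is at stake is the completeness of the safety record, not the efficacy result. Section 12.2.5 has the DMC review all SAEs, and section 12.2.3.1 sends unexpected and related SAEs to the ethics committee within 15 days. If sites follow the stated window, neither body need receive events from this biopsy. A later statement that participation caused no related SAEs would be silent about the one invasive procedure the trial adds before allocation. Women who have the VACB and are then excluded carry that risk without entering the comparison.

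**Working it through.** No arithmetic applies, and the protocol states no figure to reproduce. The check is to put the steps in order and see where the window opens under each meaning of study entry.

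**Order for a woman diagnosed by small volume biopsy only (sections 4, 5.2, 5.3, 5.5, 6.1 and 6.2):** Consent Form A; VACB; local confirmation of non-high grade DCIS; registration and issue of the trial number; central histopathology review; Consent Form C; randomisation.

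**Where study entry could fall:**

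| Meaning | Support in the protocol | Form A VACB |
|---|---|---|
| Randomisation | Schedule of Events: the Study Entry column holds consent for randomisation, baseline questionnaires and randomisation, while local diagnosis and registration are under Screening. Section 6.2.1 speaks of consent for trial entry after central review, and section 6.2.2 issues confirmation of trial entry after randomisation. Section 7.2.5 has "as for the diagnostic slides pre-study entry", although those slides are submitted after registration (section 6.1.3). | Before the window |
| Completed registration | Section 6 treats registration as the first of two stages of entry. | Before the window: section 4 applies the criteria at registration, the histology criterion needs the VACB result, and section 5.2 makes that diagnosis a precondition of trial entry |
| Start of the registration process, or signature of Form A | Section 5.2 makes the VACB part of registration. Section 11.1.1 describes the diagnostic blocks, VACB included, as coming from study entry. | Inside the window, but no section says that it starts here |

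**What happens to a VACB complication on the first two readings:**

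- *It resolves before randomisation in a woman who is later randomised.* The Schedule of Events marks related AE review only after randomisation and in years 1 to 5. Section 13.1 lists no adverse event item for the Eligibility Checklist or the Registration, Randomisation and Baseline forms.
- *The local VACB result makes her ineligible.* She is not registered. The trial number is issued at registration (section 6.1.2), so she has none.
- *She is registered but fails central review.* She has a trial number, an Eligibility Checklist and a Registration Form, but no adverse event item and no open window.
- *She is eligible but declines randomisation.* She never reaches the post-randomisation AE review.
- *The complication persists after randomisation.* It may be picked up at the later AE review.

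**How a serious case would be classed.** In section 12.1.2.2, haematoma, wound infection and seroma are expected only when they result from primary breast surgery. VACB complications are not listed. That section says its list is not exclusive, but section 12.2.2 and Appendix 1 tie expectedness to what the protocol names. If judged related, a serious VACB complication would therefore be unexpected and related, which is the class due to the ethics committee under section 12.2.3.1.

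**The case against.** The strongest reply is that study entry need not mean randomisation. Section 6 is headed Trial Entry and describes two stages, section 5.2 puts the VACB within registration, and section 11.1.1 ties the diagnostic blocks to study entry. Section 12.1.3 also uses two different terms for the start and the end of the window, which suggests two different events. Flowchart 1 (section 5.4), which shows this pathway, is not legible in the text available, so its order cannot be checked. This stands in part: the protocol does not settle the term, and a site could read it so as to include the VACB. But only the reading that no section states brings the VACB inside.

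A reader might infer that such harms go wholly unrecorded. The documents do not support that. Investigators document seriousness and causality of all AEs in source data (section 12). SAEs also go to the investigator's own Trust, and the SAE Form is triggered by becoming aware of an event, with no stated condition of randomisation (section 12.2.1.2). The ethics committee is told at once of a significant safety issue (section 12.2.3.2). These provisions rule out a claim of zero capture. They do not move the window or create a stated route for an ordinary related event.

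A reader might also infer that all related SAEs are promised to the ethics committee. Section 12.2.3.1 promises only those that are also unexpected.

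Finally, section 1.1.3 describes VACB as standard for low suspicion microcalcification and widely used, and section 5.3 says the screening steps are routine at many sites. Where VACB is routine it is not a trial procedure, so the point is confined to women consented on Form A where it is not.

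**Conclusion.** The point holds as a defect in how the window is fixed. Its start is an undefined term, used inconsistently. On the Schedule of Events' usage, and equally if it means completed registration, it falls after an invasive procedure the trial adds. The statement in section 12.1.3 that the period should capture all harm associated with the protocol is then not met for that procedure.

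The size cannot be derived. The protocol gives neither the share of women diagnosed by small volume biopsy only nor a VACB complication rate. Purely as an assumption, shares of 10% to 50% of the 932 women to be randomised would be 0.10 × 932 ≈ 93 to 0.50 × 932 = 466 biopsies. That range counts procedures and not harms. It includes any done as routine care, leaves out women never randomised, and should not be read as an estimate. The true number may be small.

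The conclusion assumes that the VACB under Form A is a research procedure in the sense of Appendix 1, which the wording of sections 5.2, 5.3 and 5.5 supports. Because the VACB precedes allocation, the primary endpoint, the analysis and the comparison between arms are unaffected. The correction is worth making because it completes the safety record at little cost.

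**What to change.** 1. Define study entry once and use it consistently.
2. In sections 7.1.7, 7.2.8, 12.1.3 and 12.2.1.1, start the related AE/SAE window for women consented on Form A at signature of that form.
3. State when the window closes for Form A women who are not randomised, for example at notification of the local or central review result.
4. Add a matching related AE review mark in the Screening column of the Schedule of Events.
5. Allow the SAE Form to be used with a screening identifier or the trial number, and give non-serious related events before randomisation a place on a form in section 13.1.
6. Reconcile the uses of the term in the Schedule of Events and in sections 5.2, 6, 7.2.5 and 11.1.1.

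No change is needed for women consented on Form B: their diagnostic biopsy is already done, Sheet B covers only the slide review, and they undergo no trial procedure before randomisation.

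The cost is wording in a few sections, one schedule mark and a few extra AE/SAE forms. No visit or procedure is added.

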12.2 Reporting Procedure

12.2.1 Site

12.2.1.1 Adverse Events

Related AEs experienced from study entry until 5 years post-randomisation should be reported in the AE section of the CRF.

AEs will be reviewed using the Common Terminology Criteria for Adverse Events (CTCAE), version 4.0 (see Appendix 2). Any related AEs experienced by the patient but not included in the CTCAE should be graded by an Investigator and recorded on the CRF using a scale of (1) mild, (2) moderate or (3) severe. For each sign/symptom, the highest grade observed since the last visit should be recorded.

